9 ASSESSMENT OF SAFETY

9.1 Specification of Safety Parameters

Parameters used to assess safety will include AEs spontaneously reported by the participant or observed by the investigator, solicited AEs captured by interviewing the child's parent or legal guardian, and events recorded from oral cavity examination. All AEs will be coded by system organ class and preferred term according to the terminology of the Medical Dictionary for Regulatory Activities (MedDRA®).

Monitoring of AEs will be conducted throughout the trial. All AEs, SAEs, and UPs will be captured any time after informed consent is obtained. In addition, all AEs will be captured until 7 days after the last day of trial participation. Serious adverse events (SAEs) will be captured until 30 days after trial participation. SAEs will be reported to the IND sponsor and to NIDCR within 24 hours of becoming aware of the event. Safety events will be reported to the sIRB according to their policies and guidelines. AEs will be followed until they are resolved, considered stable, the subject is lost to follow-up, or the AE is otherwise explained.

Cavitated caries lesions will have signs of progressing infection (e.g., abscess, fistula, etc.) recorded. Gingival tissue irritation (e.g., ulcerations and mucosal erythema, leukoplakia or darkening of pigmentation) will also be recorded. In addition we will record observed or reported: nausea, not eating, vomiting, difficulty swallowing or breathing, swelling around the lips or skin of the face, itchiness around the lips or skin of the face, hives or rash, stomach ache; or diarrhea.

Potential adverse reactions to the trial drug include

- Infection: Infection will be defined by changes in clinical signs (from examination) over time in each trial arm. The clinical criteria for the positive recording of infection are the clinical presence of swelling, dental abscess, or fistula. Assessments for infection are made at each clinical trial visit and unscheduled/emergency visit. (See Appendix E).
- Mucosal irritancy: children in each group experiencing gingival erythema, ulcerations, etc. will be recorded (See [Section 8.1.1](#) and Appendix E).
- Systemic effects/allergic reaction: children in each group reported or observed to have: nausea, not eating, vomiting, difficulty swallowing or breathing, swelling around the lips or skin of the face, itchiness around the lips or skin of the face, hives or rash, stomach ache, or diarrhea (See Appendix E).

9.1.1 Adverse Events

An adverse event is any untoward or unfavorable medical occurrence in a human subject, including any abnormal sign (for example, abnormal physical exam or laboratory finding), symptom, or disease, temporally associated with the participant's participation in the research, whether or not considered related to the participant's participation in the research.

9.1.2 Serious Adverse Events

A serious adverse event (SAE) is an AE one that meets one or more of the following criteria:

- Results in death
- Is life-threatening (places the participant at immediate risk of death from the event as it occurred)
- Results in inpatient hospitalization or prolongation of existing hospitalization
- Results in a persistent or significant disability or incapacity
- Results in a congenital anomaly or birth defect

- An important medical event that may not result in death, be life threatening, or require hospitalization may be considered an SAE when, based upon appropriate medical judgment, the event may jeopardize the participant and may require medical or surgical intervention to prevent one of the outcomes listed in this definition.

9.1.3 Unanticipated Problems

The Office for Human Research Protections (OHRP) considers unanticipated problems involving risks to participants or others to include, in general, any incident, experience, or outcome that meets **all** of the following criteria:

- unexpected in terms of nature, severity, or frequency given (a) the research procedures that are described in the protocol-related documents, such as the IRB-approved research protocol and informed consent document; and (b) the characteristics of the participant population being studied;
- related or possibly related to participation in the research (“possibly related” means there is a reasonable possibility that the incident, experience, or outcome may have been caused by the procedures involved in the research); and
- suggests that the research places participants or others at a greater risk of harm (including physical, psychological, economic, or social harm) than was previously known or recognized.

9.2 Time Period and Frequency for Event Assessment and Follow-Up

Adverse events will be followed until they have resolved, are considered stable, the participant is lost to follow-up, or the AE is otherwise explained. Phone calls or extra visits may be performed to follow up the AE. The participant will be questioned on the AE and whether it continues or is resolved at the time of the trial visit, and whether the participant received any treatment or medications specifically for the AE. The AE data will be updated and a follow-up report will be submitted to the IND Sponsor, NIDCR, and the SIRB according to the requirements of each.

At the last scheduled visit, the investigator will instruct each participant to report any subsequent event(s) that the participant, or the participant’s personal physician, believes might reasonably be related to participation in this trial. The investigator will notify the IND sponsor, NIDCR, and the SIRB of any death or AE occurring at any time after a participant has discontinued or terminated trial participation, if the death or AE may reasonably be related to this trial.

9.3 Characteristics of an Adverse Event

All AEs must be graded for relationship to trial product, expectedness, and severity.

9.3.1 Relationship to Trial Intervention

The clinician’s assessment of an AE’s relationship to test article is part of the documentation process, but it is not a factor in determining what is or is not recorded in the trial database. If there is any doubt as to whether a clinical observation is an AE, the event should be recorded. All AEs will be recorded and reported periodically to the DSMB, NIDCR, and IND sponsor, and only those which meet the definition of an unanticipated problem will be reported to the SIRB within 5 days. All AEs must have their relationship to trial product assessed using the following terms:

1. Related (Possible, Probable, Related)
 - a. The event is known to occur with the trial intervention.
 - b. There is a temporal relationship between the intervention and event onset.
 - c. The event abates when the intervention is discontinued.

- d. The event reappears upon a re-challenge with the intervention.
- 2. Not Related (Unlikely, Not Related)
 - a. There is no temporal relationship between the intervention and event onset.
 - b. An alternate etiology has been established.

9.3.2 Expectedness of AEs

The Trial PI will be responsible for determining whether an AE is expected or unexpected. An adverse event will be considered unexpected if the nature, severity, or frequency of the event is not consistent with the risk information previously described for the intervention.

9.3.3 Severity of Event

Severity of AEs will be graded according to the following scale:

- Mild: no intervention required; no impact on activities of daily living
- Moderate: minimal, local, or noninvasive intervention indicated; moderate impact on activities of daily living
- Severe: significant symptoms requiring invasive intervention; participant seeks medical attention, needs major assistance with activities of daily living. This also includes events that are considered life-threatening or may result in death.

9.4 Reporting Procedures

9.4.1 Unanticipated Problem Reporting to IRB and NIDCR

Incidents or events that meet the OHRP criteria for unanticipated problems require the creation and completion of an unanticipated problem report form. OHRP recommends that investigators include the following information when reporting an adverse event, or any other incident, experience, or outcome as an unanticipated problem to the IRB:

- appropriate identifying information for the research protocol, such as the title, investigator's name, and the IRB project number;
- a detailed description of the adverse event, incident, experience, or outcome;
- an explanation of the basis for determining that the adverse event, incident, experience, or outcome represents an unanticipated problem;
- a description of any changes to the protocol or other corrective actions that have been taken or are proposed in response to the unanticipated problem.

To satisfy the requirement for prompt reporting, unanticipated problems that are not SAEs will be reported using the following timeline:

- Unanticipated problems will be reported to the sIRB within 5 days of the investigator becoming aware of the event.
- All unanticipated problems should be reported to appropriate institutional officials (as required by an institution's written reporting procedures), the supporting agency head (or designee), and OHRP within one month of the IRB's receipt of the report of the problem from the investigator.

Concurrently with reporting to the IRB, all unanticipated problems will be reported to the NIDCR via Rho Product Safety (EDC notification).

General questions about UP reporting to the NIDCR can be directed to the Rho Product Safety Help Line (available 8:00AM – 5:00PM Eastern Time):

- US: [name]
- International: [contact]

In the event EDC is not available, the site Investigator should call Rho Product Safety to report the event, then submit a paper UP form via email or fax. Once EDC is operational, the Investigator is to enter the UP data into the EDC system within 24 hours of regained functionality.

9.4.2 Serious Adverse Event Reporting to IND Sponsor and NIDCR

Any AE meeting the specified Serious Adverse Event criteria, whether related or unrelated, will be communicated to the IND sponsor via telephone within 24 hours of site awareness:

SAE Reporting Contact Information:

- IND Sponsor: [contact]

Concurrently with reporting to the IND Sponsor, the Investigator will submit an SAE form (eCRF) to the NIDCR via Rho Product Safety (EDC notification). Once submitted, Rho Product Safety will send a confirmation email to the investigator within 1 business day. The Investigator should contact Rho Product Safety if this confirmation is not received. This process applies to both initial and follow-up SAE reports.

In the event EDC is not available, the site Investigator should call Rho Product Safety to report the event, then submit a paper SAE form via email or fax. Once EDC is operational, the Investigator is to enter the SAE data into the EDC system within 24 hours of regained functionality.

SAE Reporting Contact Information:

- Product Safety Fax Line (US): [name]
- Product Safety Fax Line (International): [contact]
- Product Safety Email: [contact]

General questions about SAE reporting to the NIDCR can be directed to the Rho Product Safety Help Line (available 8:00AM – 5:00PM Eastern Time):

- US: [name]
- International: [contact]

All SAEs will be followed until resolution or stabilization.

9.4.3 Reporting of Safety Events to FDA

Following notification from the investigator, the IND sponsor will notify FDA of any unexpected fatal or life-threatening suspected adverse reaction within 7 calendar days after the sponsor's initial receipt of the information. The IND sponsor will notify the FDA and all investigators of 1) serious, unexpected suspected adverse reactions, 2) findings from other clinical, animal or in-vitro studies that suggest significant human risk, and 3) a clinically important increase in the rate of a serious suspected adverse reaction no later than 15 calendar days after determining that the information qualifies for reporting. All serious events designated as "not related" to trial product will be reported to the FDA at least annually in a summary format.

9.5 Halting Rules

An adverse event graded as severe that is considered to be related to trial participation will be immediately reported to the Medical Monitor and will trigger an immediate investigation to determine the next steps for the child and/or trial.

The trial may be stopped early if interim analyses provide early determination of efficacy or futility. Sample size calculations account for the use of an early stopping rule based on efficacy or futility. The interim analysis will be performed after approximately half of the sample has completed the 6-month visit.

10 TRIAL OVERSIGHT

In addition to the PI's responsibility for oversight, trial oversight will be under the direction of a Data and Safety Monitoring Board (DSMB) composed of members with appropriate expertise in pediatric dentistry, pediatrics, statistics, ethics, and other scientific disciplines. Members will be appointed by NIDCR. A copy of the DSMB charter will be provided to the FDA. The DSMB will meet at least annually to assess safety and efficacy data, trial progress, and data integrity for the trial. If safety or data integrity concerns arise, more frequent meetings may be held. The DSMB will operate under the rules of an NIDCR-approved charter that will be approved at the organizational meeting of the DSMB. The DSMB will provide recommendations to the NIDCR.

11 CLINICAL SITE MONITORING

Clinical site monitoring is conducted to ensure that the rights of human subjects are protected, that the trial is implemented in accordance with the protocol and/or other operating procedures, and that the quality and integrity of trial data and data collection methods are maintained. Monitoring for this trial will be performed by a monitor from Rho, Inc. as a subcontract from NIDCR. The monitor will evaluate trial processes and documentation based on NIDCR standards and the International Conference on Harmonisation (ICH), E6: Good Clinical Practice guidelines (GCP).

Details of clinical site monitoring will be documented in a Clinical Monitoring Plan (CMP) developed by Rho, Inc., in collaboration with the NIDCR Office of Clinical Trials and Operations Management (OCTOM) and the NIDCR Program Official. The CMP will specify the frequency of monitoring, monitoring procedures, the level of clinical site monitoring activities (e.g., the percentage of participant data to be reviewed), and the distribution of monitoring reports. Some monitoring activities may be performed remotely, while others will take place at the trial site(s). The Rho monitor will conduct monitoring activities and provide reports of the findings and associated action items in accordance with the details described in the CMP. Documentation of monitoring activities and findings will be provided to the site trial team, the trial PIs, OCTOM, and the NIDCR. The NIDCR reserves the right to conduct independent audits as necessary.

12 STATISTICAL CONSIDERATIONS

Detailed statistical procedures, listings, table shells, and figures will be provided in a separate Statistical Analysis Plan (SAP) that will be finalized before trial close-out and database lock.

12.1 Trial Hypotheses

The Primary Hypothesis:

- 38% Silver Diamine Fluoride (SDF) will arrest cavitated caries lesions (ICDAS 5 or 6) in primary teeth, measured by a change in dentin hardness, without a change in ICDAS severity score, after a single application (measured at approximately 6 months post initial application). This occurs as a result of the halting of the caries disease process, which occurs very soon after application of SDF due to its strong antimicrobial and remineralizing properties.

The Secondary Hypotheses:

- 38% Silver Diamine Fluoride (SDF) will arrest a greater proportion of cavitated caries lesions (ICDAS 5 or 6) in primary teeth after two applications, approximately 6 months apart (measured at approximately 8 months after initial SDF application).
- Lesions arrested approximately 3 months after a single application will remain stable when re-assessed at approximately 6 months.
- 38% Silver Diamine Fluoride (SDF) will decrease the proportion of children in pain, number of pain episodes associated with treated teeth for children, and pain score associated with treated teeth. The hypothesis is that SDF will do this as it is an anti-hypersensitivity agent, extremely efficient at blocking dentinal tubules, and also because it can arrest cavitated lesions, and thus decrease pain.

The Tertiary Hypotheses:

- 38% Silver Diamine Fluoride (SDF) will increase Oral Health-Related Quality of Life (OHRQoL) as a result of decreasing pain and arresting caries lesions.
- 38% Silver Diamine Fluoride (SDF) will be an acceptable treatment by parents/guardians of young children.

12.2 Sample Size Considerations

The population will be children 12-71 months of age at the baseline caries examination attending early childhood education programs or recruited from clinics associated with the Michigan, Iowa or New York clinical trial sites. We anticipate 10% attrition over the trial period, as we will follow children over approximately 8 months.

The primary outcome of this trial is the proportion of arrested caries lesions approximately 6 months from the baseline visit (i.e., lesions that have changed from soft to hard over the trial period according to the ICDAS II activity criteria). A 10% difference in the proportion of arrested caries lesions between the SDF and placebo groups will be considered clinically significant. Prior studies in the literature of SDF using this outcome in primary cavitated lesions have shown a wide range for the proportion of arrested caries lesions for both SDF-treated and placebo-treated or untreated lesions; therefore the 10% difference in proportions was calculated assuming 55% versus 45% arrested caries lesions for SDF compared to placebo. In prior studies, an average of 4 lesions was treated per participant, with a within-participant correlation of 0.5; we are conservatively assuming 3 lesions per participant. The sample size calculations used a 2-sided test for a difference in proportions with cluster randomization (participant as the cluster) at significance level $\alpha=0.1\%$, with 80% power to detect a superiority difference of 10% for SDF compared to placebo. The calculations also account for the use of an early stopping rule for efficacy and futility. The interim analysis will be performed after approximately half of the sample has completed the 6-month

examinations. A Lan-Demets spending function with an O'Brien-Fleming type boundary will be used, with p-values for efficacy at 0.000001709 and 0.00099938 at 50% and 100% completion, respectively. Non-binding p-values for stopping due to futility at 50% and 100% completion will be 0.2336928 and 0.00099938, respectively. With the above assumptions, the trial will require 1144 participants to be enrolled. Sample size calculations were made using East version 6.

Sample size for the 24-48 h post-treatment safety visit is justified based on the 95% upper bound for the difference in 'safety event' between SDF and control. Erythema and 'adverse event' rate in previous studies are around 10-15% in the controls. Thus, assuming no safety difference between the two groups, and events occurring in 15% of the participants, the study sample will produce an upper bound for the difference at most 4% above the observed difference. Sample size calculations were made using PASS 13.

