5.3 Strategies for Recruitment and Retention

5.3.1 Recruitment

The New York University site will focus on providing a population that is largely Hispanic and Asian, the Iowa site will provide a population primarily White, and the Michigan site will provide a large percentage of Black and Hispanic children. It is expected that a recruitment period of 4 years should be sufficient to approach and recruit the number of participants needed. Untreated caries rates in children age 24-60 months nationwide are 10%, with 23% with some caries experience (Dye et al., 2015). Anderson et al (2010) reported 23% of children in Head Start programs in New Hampshire to have caries lesions that needed treatment (and thus were cavitated), and stated this was similar to the rest of the country. Based on preliminary experience, it is anticipated approximately half of these children with untreated caries will meet eligibility criteria for the trial. Thus, an approach: enrollment ratio of 100:12 is estimated. To enroll 1,144 children, an estimated 9,534 will be approached.

Recruitment at a variety of school-based early childhood education programs, such as Head Start, Early Head Start, and city/state subsidized preschool programs, and clinics associated with the clinical sites, will help achieve a racially and ethnically diverse population.

In the case of Head Start programs, children must present proof of a dental "examination" within 90 days of enrollment (generally September through November). This "examination" collects reportable data required for early childhood education programs on presence of untreated caries lesions (i.e., cavitated lesions) and caries experience (i.e., restorations).

As this dental "examination" may occur during the school day when parents/legal guardians are not present, the trial teams will coordinate with schools so that when the "screening" results are sent home, trial information and invitation to schedule a baseline trial visit will be sent home with the child as well. Interested families can then return their contact information to the center or call the trial team. In addition, the trial team will request a waiver of consent and waiver of HIPAA from the IRB of record to use the pre-screening data to identify children with potentially-eligible carious lesions and to ask the early childhood education program to obtain their phone number to contact these families.

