4. SAMPLE SIZE

The population will be children 12-71 months of age at the baseline caries examination attending early childhood education programs or recruited from clinics associated with the Michigan, Iowa or New York clinical trial sites.

The primary outcome of this trial is the proportion of arrested caries lesions approximately 6 months from the baseline visit (i.e., lesions that have changed from soft to hard over the trial period according to the ICDAS II activity criteria). A 10% difference in the proportion of arrested caries lesions between the SDF and placebo groups will be considered clinically significant. Prior studies in the literature of SDF using this outcome in primary cavitated lesions have shown a wide range for the proportion of arrested caries lesions for both SDF-treated and placebo-treated or untreated lesions; therefore the 10% difference in proportions was calculated assuming 55% versus 45% arrested caries lesions for SDF compared to placebo. In prior studies, an average of 4 lesions was treated per participant, with a within-participant correlation of 0.5; we are conservatively assuming 3 lesions per participant. The sample size calculations used a 2-sided test for a difference in proportions with cluster randomization (participant as the cluster) at significance level $\alpha=0.1\%$, with 80% power to detect a superiority difference of 10% for SDF compared to placebo. The calculations also account for the use of an early stopping rule for efficacy and futility. The interim analysis will be performed after approximately half of the sample has completed the 6-month examinations. A Lan-Demets spending function with an O'Brien-Fleming type boundary will be used, with p-values for efficacy at 0.000001709 and 0.00099938 at 50% and 100% completion, respectively. Non-binding p-values for stopping due to futility at 50% and 100% completion will be 0.2336928 and 0.00099938, respectively. With the above assumptions, the trial will require 1144 participants to be enrolled. Sample size calculations were made using East version 6.

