The primary method for handling missing data for 6-month and 8-month efficacy analysis will be to use a multiple imputation analysis. Missing data follow a non-monotone missing pattern. The imputation will use fully conditional specification (FCS) methods. Imputations for lesion arrest and lesion pain will be based on race/ethnicity, gender, age, trial site, initial ICDAS score, tooth location, and lesion arrest results from prior visits using a logistic regression model. Imputations for the subject-level pain score and family outcomes will be based on race/ethnicity, gender, age, trial site, maximum initial ICDAS score for the subject, a non-arrested/arrested indicator for the subject (non-arrested if any of the subject’s study lesions are not arrested) at the ‘current’ visit or at the most recent prior visit if the ‘current’ visit is missing, and results at prior visits for the

outcome using a predictive mean matching model. Missing at random (MAR) will be assumed. Twenty-five imputed datasets will be created, and results from the analyses performed on each imputed dataset will be combined using standard methods via Proc MIAnalyze.

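### Protocol 12.2 anticipates 10% attrition, but 1144 is the number needed with no loss at all; complete-case power at the planning inputs is about 77% at 5% loss by month 6 and 74% at 10%.

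*Protocol*

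**What the plan says.** Protocol 12.2 (Sample Size Considerations) states an attrition assumption near the start: "We anticipate 10% attrition over the trial period, as we will follow children over approximately 8 months". It then gives the rest of the design: a "2-sided test for a difference in proportions with cluster randomization (participant as the cluster) at significance level" of 0.1%, "assuming 55% versus 45% arrested caries lesions for SDF compared to placebo", and a two-look boundary at 50% and 100% of the sample. It reports that earlier studies had "an average of 4 lesions was treated per participant, with a within-participant correlation of 0.5", but plans on 3 lesions per child as the conservative choice. It concludes: "With the above assumptions, the trial will require 1144 participants to be enrolled". It describes no inflation step and gives no separate evaluable number.

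Protocol 5.3.1 (Recruitment) uses the same figure as the enrolment target: "To enroll 1,144 children, an estimated 9,534 will be approached". Protocol section 4 (Trial Design) also gives 1144 as the number to be randomized.

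SAP section 4 repeats the calculation, "with 80% power to detect a superiority difference of 10% for SDF compared to placebo", and the 1144 to be enrolled, but leaves out the attrition sentence. On missing outcomes, SAP 6.11 says: "The primary method for handling missing data for 6-month and 8-month efficacy analysis will be to use a multiple imputation analysis". Protocol 12.4.2 and SAP 6.11.1 count lesions removed under the early exit strategy as failures, not as missing data.

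**The concern.** Attrition is listed among the assumptions, the conclusion rests on those assumptions, and the result is stated as a number to enrol. A reader will therefore take it that the 10% loss is already absorbed and that 80% power survives it. If 1144 is instead what the calculation needs from children with observed 6-month outcomes, any loss takes the trial below its stated power. The 80% would then not follow from the protocol's own assumption list.

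**Working it through.** **Inputs (Protocol 12.2; 1:1 allocation from Protocol 5.4)**

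- Arrest proportions 0.55 and 0.45, so the difference is 0.10 and the variance sum is 0.55 × 0.45 + 0.45 × 0.55 = 0.495.
- Lesions per child 3, correlation 0.5, so the design effect is 1 + (3 − 1) × 0.5 = 2.
- Two-sided alpha 0.001, power 0.80.
- Efficacy p-values 0.000001709 (z = 4.785) and 0.00099938 (z = 3.2907); interim futility p-value 0.2336928, read as two-sided (z = 1.191).

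**Step 1: fixed design, as a rough check**

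Lesions per arm if independent = (3.2905 + 0.8416)² × 0.495 / 0.10² = 845. Children per arm = 845 × 2 / 3 = 563.5, or 1127 in total. No attrition factor is used, and the result is already close to 1144.

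**Step 2: two-look design, which reproduces the stated figure**

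Numerical integration over the two looks, with the stated efficacy boundaries and the futility boundary applied, gives a drift of 4.160 for 80% power.

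Total N = 2 × (4.160 / 0.10)² × 0.495 × 2 / 3 = 1142.2

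This is 571.1 per arm, which rounds up to 572, and 572 × 2 = 1144. The stated number is reproduced exactly with no allowance for loss.

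**Step 3: could 1144 already include the 10%?**

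One route reaches it: a fixed design at one-sided 0.001 needs 1029.3, and 1029.3 / 0.9 = 1143.7. This conflicts with the stated two-sided test, with the statement that early stopping is accounted for, and with the boundaries. Lan-DeMets O'Brien-Fleming spending at 50% gives 1.7086 × 10⁻⁶ for two-sided 0.001, which matches the stated 0.000001709. For one-sided 0.001 it gives 3.263 × 10⁻⁶. The stated boundaries therefore belong to the two-sided sequential design of Step 2.

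Nor is the number inflated elsewhere. Protocol 5.3.1 gives a ratio of 100 approached to 12 enrolled, and 1144 / 0.12 = 9533.3, which is its figure of 9,534. So 1144 is the number entering the trial.

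**Step 4: complete-case power after loss, with 1144 enrolled**

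The documents give no loss figure for month 6, so a range is shown.

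| Loss by month 6 (assumed) | Children analysed | Power, 3 lesions | Power, 3 lesions, futility bound ignored | Power, 4 lesions |
|---|---|---|---|---|
| 0% | 1144 | 80.1% | 80.9% | 83.6% |
| 5% | 1087 | 77.1% | 77.9% | 80.9% |
| 7.5% | 1058 | 75.4% | 76.2% | 79.3% |
| 10% | 1030 | 73.7% | 74.5% | 77.7% |

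**Step 5: loss tolerated before power drops below 80%**

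- 3 lesions: 1 − 1142.2 / 1144 = 0.2%. With the non-binding futility bound ignored, 1 − 1127.0 / 1144 = 1.5%.
- 4 lesions: 1 − 1070.8 / 1144 = 6.4%.

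With 1030 children analysed at 3 lesions each, 80% power corresponds to a difference of about 10.5 points instead of 10.

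**The case against.** The strongest reply is that no complete-case primary analysis is planned. The primary analysis is intention-to-treat with multiple imputation that uses earlier lesion results, so the complete-case figures are a floor. This stands as a qualification. The documents do not say how much information imputation would recover. If it recovered half of what is lost (an assumption), 10% loss would behave like 1087 children and power would be about 77%. At 7.5% loss it would behave like 1101 children and power would be about 78%. Both are below 80%, and Protocol 12.2 claims no such recovery.

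Three further points have weight:

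- The 10% runs over about 8 months, so 74% applies only if all of it occurs by month 6. Loss spread evenly over time (an assumption) would be 7.5% by month 6.
- Attrition is not defined. If the 10% includes early exits, which count as failures, fewer 6-month outcomes would be missing.
- Planning on 3 lesions when earlier studies averaged 4 builds in a margin. At 4 lesions that margin covers 5% loss but not 7.5% or 10%, and it is not described as an attrition allowance.

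On practical effect, the SAP is late enough to cite FDA requests from a pre-NDA meeting, so rewording planned power cannot change conduct. Power for larger effects is also comfortable: with 1030 children it is about 85% for an 11-point difference and 92% for 12 points. Both points limit the consequence. Neither makes the stated 80% follow from the stated assumptions.

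**Conclusion.** The point holds. At the protocol's own inputs, 1144 is the evaluable sample size for 80% power and contains no allowance for the 10% attrition listed beside it. The shortfall is about 3 to 6 percentage points of complete-case power for 5% to 10% loss by month 6 at 3 lesions per child, and smaller once imputation is credited. This rests on the stated rates, correlation, lesion count and boundaries, on reading the futility p-value as two-sided, and on an assumed loss by month 6. Type I error, boundaries and analysis method are unaffected.

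The defect lies in Protocol 12.2. SAP section 4 is internally consistent, because its 1144 and 80% follow from the inputs it lists. But it omits the attrition assumption while giving the same number as the one to be enrolled, so the two documents state different assumptions for one figure.

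**What to change.** In Protocol 12.2, state that 1144 (572 per arm) is the number of children with evaluable 6-month outcomes that gives 80% power, and that it includes no attrition allowance. Add that with up to 10% loss by month 6, complete-case power at the planning inputs falls to as low as about 74%, before any partial recovery through multiple imputation. Put the same statement in SAP section 4, and carry the 10% attrition assumption there.

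This costs one or two sentences in each document. Enrolment, analysis, boundaries and type I error stay as they are. The only downside is a less favourable stated power.
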